allow for utilization of more severely injured subjects; "task-specific" as the robotic limb trajectory mirrors a normal gait pattern, and "keep it going" as the ability to use the device out of the classic rehabilitation setting will allow for greater duration of use.

It is anticipated that modifications to the hardware and software will be developed and implemented throughout the testing of the device as required to better meet the needs of subjects. Some of these modifications that already exist include a sagittal plane actuated ankle, a passive hip frontal plane degree of freedom, a passive hip rotation degree of freedom, and a leg with reduced actuation for higher functioning subjects. Each of these modifications maintains the current safety features included in the existing manufactured device. These safety features include mechanical hardstops to limit the range of motion to less than a non-disabled person's range of motion, redundant position sensing at all actuated joints, monitoring of sensors to identify device failures prior to injury, and padding at all points where the subject and device make contact. All future device modifications will hold to these design safety features.

5. Fawcett JW, Curt A, Steeves JD. Guidelines for the conduct of clinical trials for spinal cord injury as developed by the ICCP panel: spontaneous recovery

Protocol Name:	Investigational Study of the Ekso Bionics Powered Exoskeleton for High-Dosage Use by Individuals with Spinal Cord Injury in a Non-Clinical Environment
Principal Investigator:	[name], Sr. Controls Engineer
Primary Contact Name/Contact Info:	[name], Sr. Controls Engineer [contact] [contact]
Date Revised:	9/28/2015
Study Number:	13098-01

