6.1.14. Bone Density - DEXA Scan (Initial and 12 month)

6.2. The subject will identify an individual to spot them for safety during every moment of device use. The individual may be a relative, friend or an individual hired by the subject. The spotter will not likely be a medical professional although Ekso Bionics will consider a medical profession as a spotter. The spotter must meet the Inclusion/Exclusion criteria listed below. Ekso Bionics clinicians will train the spotter with the subject in the device over a three day period in the subject's home environment (Appendix A). The spotter must be certified as

	Protocol Name:	Investigational Study of the Ekso Bionics Powered Exoskeleton for High-Dosage Use by Individuals with Spinal Cord Injury in a Non-Clinical Environment
	Principal Investigator:	[name], Sr. Controls Engineer
	Primary Contact Name/Contact Info:	[name], Sr. Controls Engineer [contact] [contact]
	Date Revised:	9/28/2015
	Study Number:	13098-01

competent by Ekso Bionics' clinicians in order for the device to be used without an Ekso Bionics clinician present. If the spotter is not approved, the subject may locate another spotter. Due to the time commitment required of the spotter, each subject may choose to train up to two spotters during the initial spotter training sessions.

6.3. Subject training will include but is not limited to:

- 6.3.1. Informing of device functions, failure modes and common characteristics.
- 6.3.2. Safety and how to respond to various conditions including being off balance, uneven surfaces.
- 6.3.3. Device set-up and take-down
- 6.3.4. Operating the device.
- 6.3.5. Putting the device on and taking the device off.
- 6.3.6. Sitting/Standing
- 6.3.7. Walking
- 6.3.8. Balance
- 6.3.9. Using hands when in the device

6.4. Spotter training will include but is not limited to:

- 6.4.1. Informing of device functions, failure modes and common characteristics.
- 6.4.2. Safety and how to respond to various conditions including being off balance, uneven ground.
- 6.4.3. Device set-up and take-down
- 6.4.4. Operating the device.
- 6.4.5. Putting the device on and taking the device off.
- 6.4.6. Sitting/Standing
- 6.4.7. Walking
- 6.4.8. Supporting the subject

Protocol Name:	Investigational Study of the Ekso Bionics Powered Exoskeleton for High-Dosage Use by Individuals with Spinal Cord Injury in a Non-Clinical Environment
Principal Investigator:	[name], Sr. Controls Engineer

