Protocol Name:	Investigational Study of the Ekso Bionics Powered Exoskeleton for High-Dosage Use by Individuals with Spinal Cord Injury in a Non-Clinical Environment
Principal Investigator:	[name], Sr. Controls Engineer
Primary Contact Name/Contact Info:	[name], Sr. Controls Engineer [contact] [contact]
Date Revised:	9/28/2015
Study Number:	13098-01

The Investigational study will take place over the course of 36 months. Each subject will be evaluated for a minimum of 12 months during the 36 month period.

If at any point during the study, the subject must take a break from regular walking for medical or personal reasons, if the break is less than 2 month, they will be able to restart the study by notifying the principal investigator of the break and resuming use. If the break is greater than 2 months, the subject will need to be re-evaluated by an Ekso Bionics physical therapist to restart the study. In the case of a break of more than 2 months, the study clock will be considered "paused" at this point and the next evaluation after the initial re-evaluation will be 3 months later (+/- 2 weeks) if in the first year of the study and 6 months (+/- 2 weeks) after beyond the first year of the study.

11. Endpoints

11.1. At the conclusion of the 12-month training period, final measurements will be taken, both the subject and the non-clinical spotter will be interviewed or a questionnaire (Appendix C) will be provided to obtain information that will assist Ekso Bionics with further development of the device. Measurements will continue to be collected every 6 months for up to the conclusion of the study or the subject terminates his/her enrollment.

11.2. Sessions will be ended for any of the following reasons:

11.2.1. Subject decides to stop participation in the study at any time and for any reason.

11.2.2. An Ekso Bionics staff member stops the subject from taking part in this study at any time if he believes it is in the subject's best interest or if the subject does not follow the study protocol.

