11.2.3. Equipment is operating inconsistently or is deemed unsafe

Protocol Name:	Investigational Study of the Ekso Bionics Powered Exoskeleton for High-Dosage Use by Individuals with Spinal Cord Injury in a Non-Clinical Environment
Principal Investigator:	[name], Sr. Controls Engineer
Primary Contact Name/Contact Info:	[name], Sr. Controls Engineer [contact] [contact]
Date Revised:	9/28/2015
Study Number:	13098-01

11.2.4. A therapist/researcher involved feels that the subject's performance or continued usage places them at risk for injury.

11.2.5. The subject is experiencing any adverse medical condition as evaluated by the subject, clinician or spotters.

11.2.6. The subject or assistants to the subject (spotter or otherwise), deliberately or not, does not follow the study protocol or uses or permits use of the device in an unsafe manner.

11.3. If the subject, deliberately or not, does not follow the study protocol or uses or permits use of the device in an unsafe manner, the device may be returned to Ekso Bionics without financial reconciliation to the subject.

11.4. If the subject does not walk in the Ekso for a period of more than 21 days for any reason, they will be withdrawn from the investigation.

11.4.1. If the subject wishes to resume participation in the study, additional training of the subject and baseline assessments may be necessary.

12. Procedures Involved in the Human Research

12.1. The study is designed to enable Ekso Bionics to evaluate the high-dosage use of a robotic exoskeleton in the home environment by persons with spinal cord injury. The study is based on the existing Ekso device. Features will include devices and controls to emulate proper gait training, stability and walking for common daily function. The device will not allow all daily functions including bending over, squatting, toilet use, climbing up or down stairs or ramps, side stepping or backward stepping.

Protocol Name:	Investigational Study of the Ekso Bionics Powered Exoskeleton for High-Dosage Use by Individuals with Spinal Cord Injury in a Non-Clinical Environment
Principal Investigator:	[name], Sr. Controls Engineer
Primary Contact Name/Contact Info:	[name], Sr. Controls Engineer [contact] [contact]
Date Revised:	9/28/2015
Study Number:	13098-01

12.2. Since the study involves periodic observation and data collection for evaluation by Ekso Bionics clinical, engineering and marketing personnel, the testing procedures includes:

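### Sections 10 and 11.4 give incompatible outcomes for the same break in walking, and 11.4 also ends follow-up after a long device or spotter failure

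*Protocol*

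**What the plan says.** Section 10 (Study Timelines) deals with the case where "the subject must take a break from regular walking for medical or personal reasons, if the break is less than 2 month"; then "they will be able to restart the study by notifying the principal investigator of the break and resuming use". If the break exceeds 2 months, "the subject will need to be re-evaluated by an Ekso Bionics physical therapist to restart the study", the study clock is paused, and the next evaluation falls 3 months after the re-evaluation in the first year, or 6 months after it beyond that. Neither case is called a withdrawal.

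Section 11.4 (Endpoints) says that if a subject does not walk in the device "for a period of more than 21 days for any reason, they will be withdrawn from the investigation". It contains no exception. Section 11.4.1 then lets a subject who wishes to come back do so, and says that retraining and baseline assessments may be needed.

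Other parts of the protocol anticipate interruptions that are neither medical nor clearly personal. Section 11.2.3 lists "Equipment is operating inconsistently or is deemed unsafe" among the reasons for ending sessions. Section 4 expects that "modifications to the hardware and software will be developed and implemented throughout the testing of the device". Section 6 allows no use of the device without a trained spotter, and 6.2 requires certification by the sponsor's clinicians before use without one of them present. Objectives 3.3 and 3.4 ask whether home use and lay spotting are safe and effective, and 12.3.7 lists device reliability among the observations.

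**The concern.** Two rules in force at the same time give the same subject two different statuses. One keeps the subject in the study, with at most a paused clock. The other takes the subject out. Nothing says which prevails, so the visit schedule and the baseline for a subject with a long break depend on which section staff happen to apply.

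The second part concerns interruptions caused by the things under study. An equipment outage of more than 21 days falls under 11.4, and Section 10 offers no route back. Loss of a certified spotter falls under 11.4 too, and under Section 10 only if it counts as a personal reason, a term the protocol does not define. In both cases, poor performance of the device or of lay spotting leads to the end of that subject's assessments. Missing data of that kind are related to the outcome, and the later visits would tend to come from subjects whose device and spotter kept working.

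**Working it through.** No figure in the plan needs reproducing. The check sets the two rules side by side and adds some day counting.

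**1. The two rules by type and length of gap.** Two months is about 59 to 62 days.

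| Gap without walking | Section 10 | Section 11.4 |
|---|---|---|
| Medical or personal, up to 21 days | notify and resume | not triggered |
| Medical or personal, day 22 to about day 59–62 | notify and resume | withdrawn |
| Medical or personal, over 2 months | re-evaluate, clock paused | withdrawn |
| Equipment outage, over 21 days | not covered | withdrawn |
| Loss of certified spotter, over 21 days | covered only if personal | withdrawn |

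Rows 2 and 3 are the contradiction. Row 2 alone spans 59 − 21 = 38 to 62 − 21 = 41 days, and row 3 has no upper limit. Rows 4 and 5 are the gaps in Section 10's cover.

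**2. Does 11.4.1 remove the conflict?** Only in part. Under Section 10 a break of under 2 months requires notification alone, and a longer one shifts the date of the next evaluation. Under 11.4.1 return depends on the subject's wish and may bring new baseline assessments. If a new baseline replaced the old one, the series of changes at 3, 6, 9 and 12 months would be broken, and the protocol does not say which baseline would count.

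**3. How far can a spotter cause a gap of more than 21 days?** Section 7.3.7 requires availability on at least four days a week in at least five of every six weeks.
- Six-week blocks taken end to end: two adjacent off-weeks plus up to 3 off-days on each side, 3 + 14 + 3 = 20 days.
- A rolling six-week window: 3 + 7 + 3 = 13 days.

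Both are below 21. A spotter-caused gap long enough to trigger 11.4 therefore means that 7.3.7 was already not being met. Section 6.2 also lets each subject train two spotters at the outset. The sentence "If the spotter is not approved, the subject may locate another spotter" concerns a spotter who fails certification; I found no corresponding provision for a certified spotter who is later lost. Section 16.8 does name spotter injury as a risk.

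**4. What one withdrawal costs.** Section 9 allows 2 to 12 subjects. One subject is 1/12 = 8% at the maximum and 1/2 = 50% at the minimum. Bone density is planned only at baseline and 12 months, so a withdrawal before month 12 without return leaves no change to estimate for that subject.

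**5. Frequency.** The protocol gives no rate of long equipment or spotter interruptions. Purely as an assumption, let p be the chance per subject over 12 months, independent between 12 subjects. The expected number is 12p and the chance of at least one is 1 − (1 − p)^12.
- p = 0.05: 0.6 subjects, 46%.
- p = 0.10: 1.2 subjects, 72%.
- p = 0.20: 2.4 subjects, 93%.

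These show how the count responds to p. They are not evidence of how often it would happen.

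**The case against.** The strongest reply is that the second part is a design preference. Objective 3.1 concerns high-dosage use, and a sponsor may reasonably remove subjects who are not walking. Device and spotter failures are also captured elsewhere: weekly device data (12.2.2), a daily log sent at least monthly (12.2.8), review meetings at least every three months (6.6), the evaluations promised in 6.5, and device reliability under 12.3.7. No multi-week outage is described anywhere, and the lead-in to 11.2.3 speaks of ending sessions. All of this stands, and it limits the point. It does not recover the 6.1 assessments that fall after a withdrawal, and it does not touch the contradiction.

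One could also try to harmonise the sections by reading Section 10's break as reduced walking, with some session at least every 21 days. Its reference to resuming use tells against that, because it presupposes that use had stopped.

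Some stronger readings are tempting and should not be adopted:
- *That the two rules divide the cases, with Section 10 protecting medical and personal breaks and 11.4 catching the rest.* Section 11.4 applies whatever the cause, so it takes in those breaks too. That overlap is the main defect.
- *That a device failure is recorded as a subject's withdrawal.* The status is withdrawal, but the protocol fixes no coding of the reason, and the log form in Appendix D is only listed.
- *That all later data are lost for good.* Section 11.4.1 allows return.
- *That results would be reported only from subjects whose device and spotter worked.* Nothing excludes data collected before withdrawal, and the handling of withdrawn subjects may lie in an analysis plan not shown.

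**Conclusion.** The contradiction between Sections 10 and 11.4 is established by the text and needs no assumption: any medical or personal break of more than 21 days is both permitted and a ground for withdrawal.

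That 11.4 would also end follow-up after a long equipment outage follows from its plain wording, taking withdrawal from the investigation to end the scheduled assessments. For spotter loss the conclusion is weaker, because that might count as personal and already implies that 7.3.7 was not met.

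The resulting loss would be related to device and spotter performance and could favour the device. Its size cannot be stated. This is an inexpensive correction worth making in a study of at most 12 subjects; it does not show that the results would be materially biased.

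**What to change.** - Reconcile Sections 10 and 11.4 so that a given break has one stated consequence, and say how equipment-caused and spotter-caused gaps are handled. The choice of interval, and of when and whether walking resumes, belongs to the sponsor and its clinicians; this review takes no position on it.
- State that an interruption of device use does not by itself end the scheduled 6.1 assessments for subjects who still consent. Say which calendar those assessments follow when the clock is paused, and which baseline is used after a return under 11.4.1.
- Record the cause and length of every interruption, and report those due to the device or the spotter as outcomes under objectives 3.3 and 3.4.

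The cost is amended wording in both sections, a cause field if the existing forms lack one, and a few visits already on the schedule for subjects who are not walking. Data from those periods should be identified as such in the high-dosage analysis, so that they are not read as the effect of continued use.

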12.2.4. Length of steps

12.2.5. Speed

12.2.6. Walking mode used

12.2.7. Battery usage

12.2.8. A minimum monthly transmittal of a usage log completed daily by both the subject and the spotter. The log will include subjective and objective data including (Appendix D):

12.2.8.1. Amount of sleep the previous night

12.2.8.2. Any deviations from typical daily activity (e.g., medications, exercise, travel, illness)

12.2.8.3. Description of physical activity other than using the Ekso.

12.2.8.4. Subjective rating of quality of life

12.2.8.5. General impressions in relation to the experience of using Ekso on a daily basis

12.2.9. The participant will be asked to use the device in their own discretion as long as the use adheres to the safety protocols outlined. Device features such as step length, swing time, and assist mode (maximum assist vs. variable assist) can be locked to prevent inadvertent or intentional manipulation of device settings which may create unsafe walking.

12.3. Notable observations by Ekso Bionics will include:

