Protocol Name:	Investigational Study of the Ekso Bionics Powered Exoskeleton for High-Dosage Use by Individuals with Spinal Cord Injury in a Non-Clinical Environment
	Principal Investigator:	[name], Sr. Controls Engineer
	Primary Contact Name/Contact Info:	[name], Sr. Controls Engineer [contact] [contact]
	Date Revised:	9/28/2015
	Study Number:	13098-01

Investigational Study of the Ekso Bionics Powered Exoskeleton for High-Dosage Use by Individuals with Spinal Cord Injury Walking in a Non-Clinical Environment

1. Investigator

Facility PI: [name], Sr. Controls Engineer, Ekso Bionics

2. Date Revised

September 28, 2015

3. Objectives

- 3.1 To determine the physiological effects of high-dosage use of the Ekso device over a 12- 36-month period.
- 3.2 To documents the quality of life benefits of using an Ekso device in a non-clinical setting.
- 3.3 To define the safety and efficacy of using the device in a home environment.
- 3.4 To determine the safety and efficacy of a non-medical professional spotting the subject.
- 3.5 To determine inclusion/exclusion criteria for an Ekso Bionics device used in a home setting.

4. Background

The incidence of spinal cord injury is estimated at 1.5-5.3 million worldwide.⁽¹⁾ "Will I walk again?" is often cited as one of the more common questions, with the decreased ability to walk as one of the most difficult challenges to live with.^(2,3) Over the last 10 years more research has focused on the ability for the spinal cord to "heal" itself, i.e. undergo plasticity,^(4,5) by task-specific, high-

	Protocol Name:	Investigational Study of the Ekso Bionics Powered Exoskeleton for High-Dosage Use by Individuals with Spinal Cord Injury in a Non-Clinical Environment
	Principal Investigator:	[name], Sr. Controls Engineer
	Primary Contact Name/Contact Info:	[name], Sr. Controls Engineer [contact] [contact]
	Date Revised:	9/28/2015
	Study Number:	13098-01

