found a worsening of urodynamic function following ambulation in a reciprocating-gait orthosis. A recent review on the physiological benefits of ambulation following SCI provided 2 conclusions from the literature: 1) the current evidence is controversial and mostly anecdotal; 2) physiological benefits of walking after SCI were most evident when ambulation was performed for at least 4-5 hours per week and over a long period of time ⁽¹⁹⁾.

[figure not shown]
Currently there is no cure for spinal cord injury ⁽²⁰⁾ however there have been improvements in therapies that promote a greater chance for neurological recovery. The evidence supporting gait training in spinal cord injuries suggests that starting early, utilizing task specific activities, and continuing the activities for long durations are beneficial. ⁽²⁰⁾ CONT training offers task specificity, however is labor intensive, time consuming, and requires a high degree of expertise to avoid injury. Moreover, those that are more severely impaired cannot begin CONT training early or safely offering a potential benefit of BWST in this subpopulation. BWST requires larger physical space for the treadmill can only be found at specialty centers and cannot be utilized at home. Therefore there is an opportunity to develop a "hybrid" of these 2 training paradigms. One that can allow for early participation despite severity of injury, can reduce the intensity of therapy assistance, can optimize the benefit of over ground training, and has the potential to be utilized in the home setting.

Recently the benefit of body weight supported training, either therapy assisted or robotically, has been questioned to be no greater than conventional over the ground training. ⁽²¹⁾ However, traditional training for those subjects with severe injuries is very labor intensive and difficult. Technology that blends the "labor reduction" benefit of BWST and the task specific benefit of over the ground training may provide the optimal solution. Therefore development of technologies that are easier to use, cheaper to implement and more

	Protocol Name:	Investigational Study of the Ekso Bionics Powered Exoskeleton for High-Dosage Use by Individuals with Spinal Cord Injury in a Non-Clinical Environment
	Principal Investigator:	[name], Sr. Controls Engineer
	Primary Contact Name/Contact Info:	[name], Sr. Controls Engineer [contact] [contact]
	Date Revised:	9/28/2015
	Study Number:	13098-01

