This is a 36 month exploratory Investigational Study compliant with the NSF Human Subjects regulations (45 CFR 690) trialing a new device for the SCI populations to aid in ambulatory function in a home setting. Ekso Bionics will enable up to twelve (12) subjects with SCI to use an Ekso device in their home for a 12-month period. Qualified subjects will help Ekso Bionics determine the practical use of the device in the home environment and will enable Ekso Bionics to gather data to develop a device for use in a home environment. The study will require a trained spotter to be present at all times that the device is being used. The study will also evaluate the effectiveness of a non-medically licensed spotter to assist the subject.

6.1. The study will measure and evaluate the following to enable Ekso Bionics to determine the physiological benefits of high-dosage use of the device in the home. Baseline measures will be recorded at the beginning of the study and reassessed a minimum of every three months over a twelve month period (+/- 2 weeks) and every 6 months after (+/- 2 weeks). The metrics include:

- 6.1.1. The number of Ekso sessions completed
- 6.1.2. Number of steps taken in device (per week, average per session, whole time)
- 6.1.3. Time spent walking in device (per week, average per session, whole time)

	Protocol Name:	Investigational Study of the Ekso Bionics Powered Exoskeleton for High-Dosage Use by Individuals with Spinal Cord Injury in a Non-Clinical Environment
	Principal Investigator:	[name], Sr. Controls Engineer
	Primary Contact Name/Contact Info:	[name], Sr. Controls Engineer [contact] [contact]
	Date Revised:	9/28/2015
	Study Number:	13098-01

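### The objective is the effect of high-dosage use, but the protocol leaves use to the participant and sets no floor near the level its background cites, so low use could be reported as high dosage

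*Protocol*

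**What the plan says.** Three sections, besides the title, name the exposure:

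- Objective 3.1: "To determine the physiological effects of high-dosage use of the Ekso device over a 12- 36-month period".
- Section 6.1 introduces the list of metrics as the means to "determine the physiological benefits of high-dosage use of the device in the home".
- Section 12.1: "The study is designed to enable Ekso Bionics to evaluate the high-dosage use of a robotic exoskeleton in the home environment".

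None of them attaches hours, steps or sessions to the term.

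On how much the device is to be used, Section 12.2.9 says: "The participant will be asked to use the device in their own discretion", subject to the safety rules.

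Two rules deal with interruptions. Section 11.4 withdraws the subject on this condition: "If the subject does not walk in the Ekso for a period of more than 21 days for any reason". Section 10 says: "if the break is less than 2 month, they will be able to restart the study by notifying the principal investigator".

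The only dose figure linked to benefit is in the background (Section 4), which reports from a review that "physiological benefits of walking after SCI were most evident when ambulation was performed for at least 4-5 hours per week". The protocol does not go on to adopt that figure as a target, threshold or definition.

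**The concern.** The objective and the conduct rules describe different exposures: high-dosage use in one, and whatever use the participant chooses in the other. A subject who walks rarely complies fully with the protocol and contributes data to a study whose stated question is the effect of high dosage.

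This matters for interpretation in both directions. If little changes among subjects who mostly used the device lightly, the result could be read as high-dosage use having no effect. If light users improve, the improvement could be credited to high dosage. In neither case would objective 3.1 have been answered. With 2 to 12 subjects (Section 9), a few light users can shape the whole picture.

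**Working it through.** The protocol states no minimum dose, so there is no figure of its own to reproduce. The check compares the least use the rules allow with the level the background cites.

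**Inputs**
- Longest gap without withdrawal: 21 days (11.4).
- Ceiling on use: 6 hours per day (table of environmental conditions after Section 7; the row is labelled for the operator and is taken here to cover the subject's use).
- Level linked to benefit: 4-5 hours per week (Section 4).
- Hours per walk: not fixed in the protocol. Assumed 0.5, 1 and 2 hours, with the 6-hour ceiling as the extreme.

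**Frequency at the floor**
365/21 = 17.4 walks per year, or 7/21 = 0.33 walks per week.

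**Weekly hours at the floor** = hours per walk × 7/21

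| Hours per walk | Hours per week | Share of 5 h | Share of 4 h |
|---|---|---|---|
| 0.5 (assumed) | 0.17 | 3% | 4% |
| 1 (assumed) | 0.33 | 7% | 8% |
| 2 (assumed) | 0.67 | 13% | 17% |
| 6 (ceiling) | 2.0 | 40% | 50% |

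The last row does not depend on an assumed session length. To reach 4-5 hours per week at one walk per 21 days, each walk would have to last 4 × 3 = 12 to 5 × 3 = 15 hours, which is above the daily ceiling.

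**Range of permitted use**
The ceiling is 6 × 7 = 42 hours per week. Against the floor this is 42/2 = 21-fold with 6-hour walks and 42/0.333 = 126-fold with 1-hour walks. All of it falls under one label.

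**The floor is not settled**
Under Section 10 a break of just under 2 months needs only notification. Taking that as 60 days (assumed), repeated breaks of that length leave 365/60 = 6.1 walks per year, or 6 × 7/60 = 0.7 hours per week even at the ceiling. That is 14-18% of 4-5 hours. A break of, say, 30 days means withdrawal under 11.4 and simple resumption under Section 10.

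**Other provisions that bear on use**
Spotters must be available four days per week in five of every six weeks (7.3.7), an average of 4 × 5/6 = 3.3 days per week, ten times the floor frequency. A usage log is completed daily (12.2.8). Both make frequent use possible, and neither requires it of the subject.

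**The case against.** The best case for the protocol has four parts.

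*The setting is built for frequent use.* Spotter availability, the daily log and the log's reference to day-to-day experience with the device all suggest that regular use was expected. That is fair, and a subject at the 21-day floor all year is an extreme and not a forecast. But an expectation places no condition on whose data answer objective 3.1.

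*Dose is recorded.* Sessions, steps, walking time and mode (6.1.1-6.1.4) head the list of metrics, and device data are transferred at least weekly (12.2.2). This stands, and it is why the correction is cheap. A reader might infer that the protocol treats dose only as an outcome. The text does not support that: the schedule calls these device measures, gives them no baseline assessment, and nothing prevents their use as exposure. Equally, nothing ties them to the objective.

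*The analysis belongs in the SAP.* A reader might also infer that the protocol averages every subject's change into a single high-dosage effect. It does not say so; 14.9 leaves the methods open. How exposure enters the analysis may properly be left to a SAP. The mismatch between 3.1 and 12.2.9 cannot, because the protocol itself fixes both sides of it.

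*The study is an exploratory pilot with no hypothesis test* (Sections 6 and 15.1). That limits formal dose-response work. It does not make the label on the conclusion right.

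**Conclusion.** The point holds as a mismatch between the stated exposure and the permitted exposure. The lowest use allowed under 11.4 is at most 2 hours per week, 40-50% of the level the background relies on, and about 7-8% at an assumed 1 hour per walk. If Section 10 governs instead, it is lower still. So results from low use could be reported as the effect of high dosage; the documents do not show that they would be.

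The conclusion rests on three things: 12.2.9 read as setting no minimum, the daily ceiling read as applying to the subject's use, and the 4-5 hours per week used only as the protocol's own benchmark. That benchmark comes from a review which, as the background reports, also judged the evidence controversial and mostly anecdotal.

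It would be tempting to state by how much an effect would be diluted. The documents give no basis for this: they contain no forecast of use, no effect size and no dose-response relation.

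**What to change.** None of this imposes a dose.

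1. Reconcile 3.1, 6.1 and 12.1 (and the title) with 12.2.9 by stating the overall result as the effect of discretionary home use.
2. Reconcile 11.4 with Section 10, so that one rule governs interruptions and the record shows which subjects and periods remain in the study. Which rule applies is for the sponsor and investigator to decide.
3. Present each subject's change in 6.1.5-6.1.14 beside the achieved walking hours per week over the same interval, from 6.1.3 and the device data. For bone density the interval is baseline to 12 months.
4. Report how many subjects and how many assessment intervals reached the 4-5 hours per week cited in the background, and limit high-dosage wording to a descriptive statement about those.

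The cost is protocol wording and one added presentation of data already collected. The downside should be stated in the protocol. Achieved use is chosen after baseline, and subjects who stay healthier may walk more. With 2-12 subjects, any relation of change to hours is therefore descriptive and not causal, and the statement about high dosage may rest on very few subjects or none.
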